#### **4.4.2. Handling of participant withdrawals or early termination**

The Investigator should document the primary reason for a patient's premature withdrawal from the trial, in the patient file and in the electronic Case Report Form (eCRF). Every effort must be made to perform the protocol-specified safety follow-up procedures to capture AEs and serious adverse events (SAEs) for the whole duration of the study. Refer to section 6.1.4

#### **4.5. Lost to follow up**

A participant will be considered lost to follow-up if he or she repeatedly fails to return for scheduled visits and is unable to be contacted by the study site.

The following actions must be taken if a participant fails to return to the clinic for a required study visit:

- The site must attempt to contact the participant and reschedule the missed visit as soon as possible, counsel the participant on the importance of maintaining the assigned visit schedule and ascertain whether or not the participant wishes to and/or should continue in the study.
- Before a participant is deemed lost to follow up, the investigator or designee must make every effort to regain contact with the participant (at least 3 attempts including 1 phone call and 1 written message to the participant) and document his/her effort (date and summary of the phone call and copy of the written message in the source documents) to complete the final evaluation. All results of these evaluations and observations, together with a narrative description of the reason(s) for removing the participant, must be recorded in the source documents. The eCRF must document the primary reason for withdrawal.

Should the participant continue to be unreachable, he/she will be considered to have withdrawn from the study with a primary reason of lost to follow-up documented in the eCRF.

#### **4.6. Premature termination or suspension of study**

This study may be temporarily hold or prematurely terminated if there is sufficient reasonable cause.

Section 8.3 describes the study halting rules, specifying the number of adverse events, as well as the nature and/or the severity of events, that would trigger the temporary suspension of the study, pending a safety investigation and potential subsequent premature termination of the study.

Written notification, documenting the reason for study suspension or termination, will be provided to all involved parties.

Study may resume once concerns about safety, protocol compliance, data quality are addressed and satisfy the IEC and CA.

#### **4.7. Definition Start and End of the trial**

The start of the trial is defined as the first patient first visit (FPFV) in the trial.

The end of the trial is defined as completion of the last visit of the last patient (LPLV) in the trial.

## 5. STUDY TREATMENT

### 5.1. Study treatment and control description

Intervention name	NVDX3
Dose formulation	Vial
Unit dose Weight	4g +/- 0.1g of dry powder
Dosage level(s)	Max 1 unit dose
Route of administration	Implant surgery
Use	Experimental
IMP and NIMP	IMP
Sourcing	Provided by Novadip Biosciences
Packaging and labeling	
The IMP will be manufactured, packaged, and labeled according to Good Manufacturing Practice guidelines and in accordance with all applicable laws or regulations.
 
Each IMP carton will be labeled according to the country requirements.
 
Details of the packaging and labeling will be provided in the “NVDX3-CLN01 IMP Handling Manual”

#### 5.1.1. Formulation, appearance, packaging and labeling

The active ingredient in the NVDX3 drug substance (DS) is a lyophilized powder composed of hydroxyapatite/beta-tricalcium phosphate (HA/TCP) particles embedded in an ECM, biologically active growth factors and non-viable osteogenic cells.

The NVDX3 powder is presented in a vial (primary package) placed in a plastic bag (secondary package), both sterilized by gamma radiation.

#### 5.1.2. Product storage and stability

NVDX3 vial should be stored at room temperature (15-25°C).

The investigator or designee must confirm at receipt of the IMP the intactness of the vial and check that the temperature conditions have been maintained during transit, report any discrepancies and wait for further instructions by the Sponsor before using the IMP. All IMPs must be stored in a secure, controlled, and monitored area in accordance with the storage conditions, with access limited to the investigator and/or authorized site staff.

Any quality concern related to an IMP or temperature exposure must be immediately reported as per “NVDX3Handling Manual”.

### 5.1.3. Preparation

Before use/prior to implantation, the content of the vial [REDACTED]  
[REDACTED] must be reconstituted aseptically by the surgeon

### 5.1.4. Dosing

The total administered quantity of NVDX3 will depend on the bone defect size but cannot exceed the maximum reconstituted implant volume [REDACTED]

### 5.1.5. Route of administration/ applied surgical technique

### 5.1.6. Duration of therapy trial treatment

NVDX3 is administered during a single surgical intervention.

## 5.2. IMP accountability

The investigator is responsible for the IMP accountability, reconciliation, and record maintenance (ie, receipt, reconciliation, and final disposition of used/unused records).

The volume of NVDX3 implanted will be estimated during the surgery and by using post-op CT scans.

Refer to the “NVDX3-CLN01 IMP Handling Manual” for complete process description.

## 5.3. Prohibited medications, treatments, and procedures

Prohibited medications as per exclusion criteria are:

- Chronic, currently ongoing or planned during course of the trial, use of any medications that in the opinion of the investigator might affect bone metabolism or the quality of bone formation such as bisphosphonates, steroids, methotrexate, anticoagulant therapies, immunosuppressant therapy, or immunotherapy.
- The addition of any bone enhancing pharmacological agents (e.g., autogenous recombinant human bone morphogenetic protein-2), bone scaffolds/carriers or autologous bone, in addition to the NVDX3 graft, is not allowed.

## 6. STUDY SCHEDULE

### 6.1. Schedule of Activities Table

	Screening	Acute safety FU					Long-term safety FU			Early Termination ETV
		V1	V2 	V3	V4	V5	V6	V7	V8	
					W2	W6	M3	M6	M12	
			Implant Surgery IS (Max 7 days after DRF diagnosis)	Hospital Discharge HD	IS+13d ± 2d	IS+42d ± 7d	IS+90d ± 15d	IS+180d ± 30d	IS+360d ± 30d	
Informed consent		x								x 
Eligibility criteria		x								x 
Demography		x								
Medical and concomitant medication history		x								
Index fracture evaluation/classification		x								
Physical examination		x	x	x	x	x	x	x	x	x
Weight/Height (BMI) 		x	x	x	x	x	x	x	x	x
Triplectate 12-Lead ECG			x							x
Vital signs		x	x	x	x	x	x	x	x	x
Inspection of the skin of the affected arm 		x	x	x	x	x	x	x	x	x
Standard safety laboratory 		x		x	x	x	(x)	(x)	(x)	
Serology (HIV, HBV & HBC)		x								
Pregnancy test 		x								x
Implant Surgery (IS)			x 							
Peri-operative IS related information			x							
Grip strength test				x	x	x	x	x	x	x
NRS-pain		x		x	x	x	x	x	x	x
PRWE				x	x	x	x	x	x	x
MMWS				x	x	x	x	x	x	x
Radiological efficacy 	AP/LAT X-ray	x*	x 7*	x*	x*	x*	x*	x*	x	x
	DECT-scan	x* (Normal CT)		x			x		x	
AE/SAE collection			x	x	x	x	x	x	x	x
Concomitant medication			x	x	x	x	x	x	x	x
Concomitant therapy				x	x	x	x	x	x	x

1 In-clinic stay: The patient may be hospitalized before the surgery following to hospital standard of care. The required pre-operative assessments can be done up to 3 days before the surgery.

2 Skin inspection to evaluate potential surgical site infections.

3 At screening, Discharge, V4 and V5: safety laboratory analyses are mandatory. At V6, V7 and V8: Upon occurrence or any suspicion of safety related issues.

4 In women of childbearing potential only: a serum pregnancy test will be performed at Screening and at V8

5 Follow the instructions ad per "NVDX3 handling Manual".

6 To guarantee image quality, all X-rays and CT-scan acquisitions will need to strictly follow the imaging instructions as described per "Imaging Acquisition Manual".

7 AP/LAT X-rays: both after insertion of fixation device, and after insertion of the NVDX3 implant (at the end of the surgery)

8 Height at screening only

9 Informed consent proposing participation to the long-term safety follow-up study (NVDX3-CLNOX)

\* Standard of care image acquisitions for the diagnosis and follow-up of DRF

### 6.1.1. Screening visit

- Eligibility check
- Medical history, including diabetes and osteoporosis status
- Target DRF fracture classification according to the Distal Fracture Classification systems (Appendix 1)
- Physical examination: (Refer to section 8.1.1)
- NRS-pain (which will also be used as the reference NRS-pain to which the follow-up patient reported outcomes (PRO) will be compared)

### Screen failures

Screen failures are defined as participants who consent to participate in the clinical study but are not subsequently enrolled in the study

Individuals who do not meet the criteria for participation in this study (screen failure) may be rescreened if the reason for failure has been resolved at the time of rescreening.

Participants who have laboratory values that are marginally outside the defined range(s) for inclusion in the study may have those tests repeated once, if there is realistic chance of normalization having occurred. This should be discussed with the Sponsor Study Physician.

### 6.1.2. Implant Surgery

- For the standardized surgical technique and osteosynthesis materials used please refer to section 5.1.5 and 0

- Record (serious) adverse events as reported by the patient or observed by the investigator (including abnormal radiological observations).
- Record changes in concomitant medication as reported by the patient or prescribed by the investigator

### 6.1.3. Hospital discharge visit

The timing of the hospital discharge is at the PI's discretion taking into account the patient status. In case of any adverse events leading to hospital prolongation for any medical reason, a SAE should be completed.

This visit is considered as the reference timepoint for the safety and radiological and clinical efficacy (PRO and physician-based assessment) timepoints

#### **6.1.4. (Early) Termination visit**

If a patient ends the study prematurely (before 12 month Follow-up visit), either on own decision (withdrawal of IC or for any other reason), by decision of the investigator, for any other reason like lost to FU, or resulting from a halting rule and/or subsequent decision to terminate the study (described in more detail by the Safety Monitoring Plan) this early termination should be reported through the completion of the “End-of study Form” including the following information:

- Date of termination
- Reason for termination
- If lost to follow-up, a formal confirmation of the 3 contact attempts should be documented

#### **6.1.5. Unscheduled visit**

Additional visits as per standard of care (e.g., visits with the anesthesiologist before or after the orthopedic surgery, additional safety visit including blood sampling) are not part of the study schedule. Except for the reportable safety events (see safety reporting section for more instructions), non-safety related data generated during those unscheduled visits will not be recorded.

## 7. EFFICACY ASSESSMENTS AND- PROCEDURES

### 7.1. Study procedures/evaluations

Consecutive study visits, including clinical efficacy assessments should be conducted by the same clinician, in order to standardize that evaluation and reduce background noise (bias) as far as possible.

The patient-reported outcome (PRO) questionnaires should be completed by the patient in a quiet place prior to any discussion regarding study-related issues, disease status, or treatment effect with the investigator/site staff. The PROs will be completed by the study participant on paper at the site, during study visits. The PROs and physician completed questionnaire should be checked for completeness by the clinical staff.

#### 7.1.1. Grip strength test

Grip strength will be measured by using an hydraulic hand dynamometer with the elbow flexed 90 and the forearm in neutral rotation. Values are expressed as the percentage of the strength on the contralateral (uninjured) side.

#### 7.1.2. Physician reported Modified Mayo Wrist Score

The Modified Mayo Wrist Score (MMWS) is a modification of the Geen and O'Brien score (Appendix 4). There is a total of 100 points which are divided among the evaluator's assessment of pain (25 points), active flexion/extension arc as a percentage of the opposite side (25 points), grip strength as a percentage of the opposite side (25 points), and the ability to return to regular employment or activities (25 points).

Pain is rated as none (25 points), mild (20 points), moderate (10 points), or severe (0 points) by the evaluator, based on the patient's subjective description.

The total score ranges from 0 to 100 points with higher scores indicating a better result. An excellent result is defined as 90–100 points, good is 80–89, fair is 65–79 points, and poor is less than 65 points.

#### 7.1.3. Patient reported Numeric Rating Scale for pain

Numerical rating scales (NRSs) are the simplest and most commonly used scales. The numerical scale is most commonly 0 to 10, with 0 being “no pain” and 10 being “the worst pain imaginable.” The patient draws a circle around the number that best describes the pain dimension, usually intensity. Advantages of NRSs include simplicity, reproducibility, easy comprehensibility, and sensitivity to small changes in pain.

For more details, please refer to Appendix 5.

#### **7.1.4. Patient Reported Wrist Evaluation**

The PRWE is a 15-item questionnaire designed to measure wrist pain and disability in activities of daily living. The PRWE allows patients to rate their levels of wrist pain and disability from 0 to 10, and consists of 2 subscales:

- Pain subscale: contains 5 items each of which is further rated from 1-10. The maximum score in this section is 50 and minimum 0
- Function subscale: contains total 10 items which are further divided into 2 sections i.e specific activities (having 6 items) and usual activities (having 4 items). The maximum score in this section is 50 and minimum 0.

For more details, please refer to Appendix 6.

#### **7.1.5. Efficacy assessment by the independent central radiologists**

Besides bone formation, bone remodeling and bone union will be assessed as described in more detail in the Appendix 8 and/or the “Imaging Reading Manual”.

## 8. SAFETY ASSESSMENTS AND PROCEDURES

### 8.1. Specification of safety parameters

#### 8.1.1. Physical examination

A brief physical examination will include the assessments of the skin, respiratory system, cardiovascular system, and abdomen (liver and spleen).

- Height and weight will also be measured, Body mass index is to be calculated and recorded.
- Algodystrophy evaluation: Assessment of complex regional pain syndrome using the Budapest criteria
- Skin inspection of the affected arm, in order to evaluate the potential surgical site infections
  - Skin color (Pale/cyanotic/other)
  - Signs of local infection (yes/no)
  - Swelling (oedema) (yes/no)
  - Arm temperature (Normal/cold/hot)

Clinically relevant findings or worsening of previous findings will be recorded as AEs.

#### 8.1.2. Vital signs

Body temperature, pulse rate, respiratory rate, and BP will be assessed.

BP and pulse measurements will be assessed after 5 minutes of rest in a supine position (in a quiet setting without distractions such as a television or cell phones) with a completely automated device. Manual techniques will be used only if an automated device is not available.

Vital signs (to be taken before blood collection for laboratory tests) will consist of 1 pulse and 3 BP measurements (3 consecutive BP readings will be recorded at intervals of at least 1 minute). The average of the 3 BP readings will be recorded on the eCRF.

#### 8.1.3. Electrocardiograms

Triplet 12-lead ECG will be obtained as outlined in the Schedule of Activities

All ECG recordings should be taken with the study participant resting in the supine position for at least 5 minutes before the recording.

When ECG recording coincides with other, potentially disturbing procedures (such as blood sampling) the ECG should always be performed first, if at all possible.

#### 8.1.4. Clinical laboratory evaluations

Clinical Laboratory will be obtained as outlined in the Schedule of Activities.

List of clinical laboratory tests to be performed are:

- Hematology (Hemoglobin, Hematocrit, Red blood cells, white blood cells, platelets, neutrophils, eosinophils, basophils, lymphocytes, monocytes and erythrocyte sedimentation rate)
- Coagulation (activated partial thromboplastin time, prothrombin time-INR (Quick) (PT-INR), Fibrinogen)
- Biochemistry (NA+, K+, CL-, AST, ALT, AP, GGT, total protein, total bilirubin, CRP, Uric acid, LDH, CK, Glucose, Ca++, Phosphorus, TSH, Vit D)
- Serology (at screening only): HIV, Hepatitis B and C (HBV& HBC)

Blood testing is required up to 6 weeks post-grafting surgery supporting the evaluation of acute toxicity.

However, upon any suspicion of a safety related issue the investigator needs to define, upon his medical judgement, if any required laboratory analysis should be required. All ad-hoc clinically significant out of range laboratory assessments, will be recorded though (S)AE reporting.

The total amount of blood planned to be collected over the duration of the study will be approximately 300cc.

#### **8.1.5. Specimen preparation, handling, and storage**

All blood laboratory evaluations will be performed by the local laboratory in accordance with its standard of care preparation (including required blood volumes, the type and number of blood sampling tubes and other blood sampling materials), handling and storage procedures.

All samples will be discarded after analysis and results records

#### **8.1.6. Safety assessment by local radiologist**

In order to identify potential safety signals, the local radiologist, at each study visit involving imaging needs to fill the safety questionnaire, as outlined in appendix 7. All potential safety findings need to be entered into the patient file and clinically relevant observations should be recorded though the (S)AE reporting.

#### **8.1.7. Adverse Events and Serious Adverse Events**

##### **Definition adverse events (AE)**

Adverse event means any untoward medical occurrence associated with the use of an intervention in humans, whether or not considered intervention-related

An AE is defined as any untoward medical occurrence in a patient or clinical investigation subject administered the NVDX3 therapy and which does not necessarily have to have a causal relationship with this treatment

Events meeting the AE definition:

- Any abnormal laboratory test results (hematology, clinical chemistry, or urinalysis) or other safety assessments (e.g., radiological acquisitions, vital signs measurements), including those

that worsen from baseline, considered clinically significant in the medical and scientific judgment of the Principal Investigator (e.g. not related to progression of underlying disease).

- Exacerbation of a chronic or intermittent pre-existing condition including either an increase in frequency and/or intensity of the condition.
- New conditions detected or diagnosed after trial treatment administration even though it may have been present before the start of the trial.
- Signs, symptoms, or the clinical sequelae of a suspected drug-drug interaction.

Events NOT meeting the AE definition:

- Any clinically significant abnormal laboratory findings or other abnormal safety assessments which are associated with the underlying disease, unless judged by the Principal Investigator to be more severe than expected for the patient's condition.
- The disease/disorder being studied or expected progression, signs, or symptoms of the disease/disorder being studied, unless more severe than expected for the patient's condition.
- Medical or surgical procedure (e.g. endoscopy, appendectomy): the condition that leads to the procedure is the AE.
- Situations in which an untoward medical occurrence did not occur (social and/or convenience admission to a hospital).
- Anticipated day-to-day fluctuations of pre-existing disease(s) or condition(s) present or detected at the start of the trial that do not worsen.
- Pregnancy

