## 1.2. Risks/benefits assessment

### 1.2.1. Potential risks

Potential Risk		Comments
NVDX3	- First-in-human administration	Pre-clinically no NVDX3 related safety signals were observed. Updated safety information on NVDX3 can be consulted in the latest version of the IB.
DRF Surgery	- tendon irritation and rupture, nerve injury, malunion, nonunion, pain syndromes, loss of reduction, and posttraumatic arthritis	The surgical procedure, aiming fixation of the DRF will be performed as per standard of care of the clinical site.
General Surgery	- pain, local infection, thrombosis of the veins and orthostatic hypotension.	Prophylactic use of antalgics, prophylactic antibiotics, anticoagulants, and fluids might reduce their occurrence and frequency.
Imaging	- Risks linked to the medications given prior and during any of the study procedures	Well-known risks related to the use of sedatives, analgesics and anaesthetics
	- Radiation exposure	- DECT considered to be dose-neutral compared to conventional CT - Estimated radiation increase compared to SoCa imaging protocol for DRF remains limited

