## **AE of Special Interest (AESI)**

The following adverse events will be considered as of special interest:

- Hypersensitivity reaction
- Immunological reaction
- An AE requiring immunosuppressive medication
- Ectopic bone formation
- Tumor formation
- Treatment failure:
  - Continued non-union/Non-fusion
  - Refracture of the targeted area
  - Revision surgery/intervention including removal of NVD-X3
  - Any other condition considered by the treating physician as treatment failure

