**b) Relationship to the NVDX3 treatment**

All adverse events (AEs) must have their relationship to the NVDX3 treatment (relatedness to the NVDX3 implant, the NVDX3 implant procedure and other study or non-study related procedures) assessed by the Principal Investigator who examines and evaluates the patient based on the Investigator Brochure, the temporal relationship of the event and his/her clinical judgment. Alternative causes, such as underlying disease(s), concomitant therapy, and other risk factors will be considered and investigated. The degree of certainty about causality will be graded using the categories below.

For each AE/SAE, the Principal Investigator must document in the medical notes that he/she has reviewed the AE/SAE and has provided an assessment of causality.

There may be situations in which an SAE has occurred, and the Principal Investigator has minimal information to include in the initial report to the Sponsor. However, it is very important that the Principal Investigator always assesses the causality for every event before the initial transmission of the SAE data to the Sponsor. The Principal Investigator may change in the eCRF his/her opinion of causality in light of follow-up information: a SAE follow-up report with the updated causality assessment will be recorded in the eCRF.

As part of medical review, the causal relationship will also be assessed by the safety officer of the Sponsor or his delegate.

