## **8.2. Safety Reporting procedures**

### **8.2.1. Time period and frequency for collecting AE/SAE information**

All AEs and SAEs will be collected from the signing of the ICF until the (early) Termination Visit at the time points specified in the Schedule of Activities ([Section 6.1](#)).

Any medical condition that is present at the time of the patient’s screening will be considered as baseline and not reported as an AE. However, if the trial patient’s condition deteriorates at any time during the trial, it will be recorded as an AE.

Changes in the severity of an AE/SAE will be documented to allow an assessment of the duration of the event at each level of severity to be performed. AEs characterized as intermittent require documentation of onset and duration of each episode.

Investigators are not obliged to actively seek AE or SAE in patients after their final discharge from the study. However, if the Principal Investigator learns of any SAE, including a death, at any time after a patient has been discharged from the trial, and he/she considers the event to be reasonably related to NVDX3 or trial participation, the Principal Investigator must promptly notify the Sponsor or designee.

Prompt notification by the investigator to the sponsor of an SAE is essential so that legal obligations and ethical responsibilities towards the safety of participants and the safety of an IMP under clinical investigation are met.

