1.3 Study Endpoints

1.3.1 Primary Endpoint

The primary endpoint is the evaluation of all SAEs and NVDX3 related AEs between screening (V1) and 12 months post-IS (V8).

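### The adverse-event exclusions for the expected course of the fracture are not reconciled with the AESI list or the imaging-safety rule, so a non-serious healing failure, above all malunion or loss of reduction, can go without a causality assessment

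*Protocol*

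**What the plan says.** **Exclusions.** Protocol 8.1.7, under the AE definition, leaves out "The disease/disorder being studied or expected progression, signs, or symptoms of the disease/disorder being studied, unless more severe than expected". A second bullet removes clinically significant laboratory results and likewise "other abnormal safety assessments which are associated with the underlying disease, unless judged by the Principal Investigator to be more severe than expected". The same section counts radiological acquisitions among the safety assessments. Its inclusion bullet takes abnormal results "considered clinically significant in the medical and scientific judgment of the Principal Investigator (e.g. not related to progression of underlying disease". Protocol 8.2.1 adds that a condition present at screening "will be considered as baseline and not reported as an AE", unless it deteriorates.

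**Inclusions.** The AESI list in Protocol 8.1.7, repeated in SAP 2.4.1.5, is introduced as a list of adverse events. It names "Continued non-union/Non-fusion", refracture of the target area, revision surgery, and a final entry for anything else the treating physician regards as treatment failure. Protocol 8.1.6 has the local radiologist complete a safety questionnaire at each imaging visit and sends clinically relevant findings to (S)AE reporting.

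**Known risks.** Protocol 1.2.1 gives the risks of the surgery as "tendon irritation and rupture, nerve injury, malunion, nonunion, pain syndromes, loss of reduction, and posttraumatic arthritis".

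**What depends on recording.** "All adverse events (AEs) must have their relationship to the NVDX3 treatment" assessed (Protocol 8.1.7 b). The primary endpoint in SAP 1.3.1 is "the evaluation of all SAEs and NVDX3 related AEs between screening (V1) and 12 months post-IS (V8").

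**The concern.** The implant is placed in the fracture. Impaired healing or collapse at that site is therefore a local harm that the implant could plausibly cause, and it is also what an investigator may regard as the course of the disorder under study. The exclusions turn on whether an event is more severe than expected. This is a single-arm, first-in-human study of 10 patients, so there is no control rate against which to judge what is expected. The assessments bullet leaves that judgement to the Principal Investigator, and the disease bullet names nobody.

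Causality is assessed only for recorded AEs. A non-serious event that is screened out first never receives a relationship grade. It then cannot become a reportable AESI with 24-hour reporting (Protocol 8.1.7 and 8.2.5), and it cannot count as NVDX3-related in the primary endpoint. The rule in SAP 2.4.1.4 that treats a missing causality grade as related does not help, because it applies only to events already in the AE data.

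**Working it through.** The plan has no hypothesis, alpha or power (Protocol 9.2 and 9.5), so there is no stated figure to reproduce. The check sets the rules side by side for each kind of event.

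1. **Continued non-union or refracture.** The AESI list calls these adverse events, so on a plain reading they are recorded and graded. Against this, a fracture that simply fails to heal was present at screening and may not have deteriorated (Protocol 8.2.1). It is also neither clearly new nor clearly worse than the pre-implant state, which the TEAE definition requires (Protocol 8.1.7, SAP 2.4.1.3). The AESI outputs in SAP 4.4.1 are restricted to treatment-emergent events, so this matters for reporting as well as for recording.
2. **Revision surgery.** It is on the AESI list, yet the AE definition says that a surgical procedure is not an AE and that the condition leading to it is. The SAE text also excludes hospitalisation for elective treatment of a pre-existing condition that has not worsened, so even the serious route for revising a non-union can be argued over.
3. **Malunion and loss of reduction.** Both are named as surgical risks in Protocol 1.2.1, and Protocol 1.1.1 gives numeric limits for loss of reduction. Neither is on the AESI list by name. They reach it only if the physician calls them treatment failure.
4. **Delayed union.** It is not named among the surgical risks or on the AESI list, so it depends on the same final entry.
5. **An image showing displacement at the fracture.** Protocol 8.1.6 sends it to (S)AE reporting if clinically relevant. The assessments exclusion in 8.1.7 removes it, even if clinically significant, when it is tied to the underlying disease and not more severe than expected. Two rules give two answers for one image.
6. **Central reads.** SAP 4.3.1 and 4.3.2 tabulate continued non-union at 12 months and list alignment and fixation integrity. These are efficacy outputs, and no stated step passes a central finding to AE reporting or to causality assessment.

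**Scale at n = 10 (illustration only).** Assume that one healing event would have been judged NVDX3-related and that there is no other related event.
- Recorded: 1/10 = 10%, exact (Clopper-Pearson) 95% CI 0.3% to 44.5%.
- Not recorded: 0/10, exact 95% CI 0 to 1 − 0.025^(1/10) = 30.8%.

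The documents give no healing-failure rate. For assumed true rates p, the chance of at least one case in 10 patients is 1 − (1 − p)^10:
- p = 1%: 9.6%
- p = 5%: 40.1%
- p = 10%: 65.1%
- p = 20%: 89.3%

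**The case against.** The strongest reply is that the specific list governs the general exclusion. Non-union, refracture and revision are called adverse events in terms, and every AE needs a causality grade. A reader might infer that the protocol permits non-union to be left out. The documents do not support that: the exclusion covers only what is expected, and it brings back anything more severe than expected.

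Other points also carry weight.
- Protocol 1.2.1 presents malunion and loss of reduction as risks of surgery, which is not the same as expected progression of the fracture. The AE definition includes new conditions diagnosed after treatment, and SAP 4.4.1 provides for TEAEs related to the grafting surgery.
- Serious events enter the primary endpoint whatever their cause.
- Non-union would be visible in the central-read tables.
- The study is described as monocentric (Protocol 3.1, SAP 1.1), with at most two sites allowed for in Protocol 9.6. Inconsistency would arise mainly between cases and much less between sites.
- The content of Protocol Appendix 7 and of SAP 2.4.2 is not visible, part of SAP 2.4.1 is redacted, and the Safety Monitoring Plan is a separate document. Any of these might reconcile the rules.

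A reader might also infer that each unrecorded healing event moves the primary result by 10 percentage points. That is not so in general. The primary endpoint is descriptive and delivered as a listing, and a non-serious event counts only if it is judged NVDX3-related.

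These replies narrow the point without removing it. No visible text gives the AESI list or Protocol 8.1.6 precedence over the exclusions or over the baseline rule. The final AESI entry is itself a matter of judgement, and the central-read tables do not lead to a causality grade.

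**Conclusion.** The point holds as an unreconciled conflict between stated rules. It is not a clear licence to omit failed healing. Events named on the AESI list are AEs on a plain reading, with residual doubt over baseline status and treatment emergence. Malunion, loss of reduction and delayed union are the more exposed, because their recording depends on the physician calling them treatment failure or on a judgement that they exceed what was expected.

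The consequence is limited to non-serious healing events that are screened out. These lose their causality assessment and, with it, any route to a reportable AESI or to the primary endpoint. How often this would happen cannot be derived from the documents. The contrast of 0/10 with 1/10 applies only under the stated assumption that the missed event would have been judged related. The conclusion also assumes that no redacted or separate text settles the precedence. The correction is cheap and the study has no control group, so it should be made.

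**What to change.** Add one sentence to the exclusions in Protocol 8.1.7, for example:

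*The underlying-disease exclusions do not apply to any event on the AESI list, or to delayed union, malunion, loss of reduction or fixation failure at the implanted site. These are always recorded as adverse events and their relationship to NVDX3 is assessed.*

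In addition:
- Mirror the sentence in SAP 2.4.1 and state whether these events count as treatment-emergent when the fracture was present at screening (Protocol 8.2.1).
- Say whether a revision is recorded as the procedure or as the condition that led to it, since the AE definition and the AESI list differ.
- State how a local or central imaging finding of failed healing is passed to AE reporting.

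Keep the exemption to these named events. Ordinary post-fracture pain and swelling should stay under the existing rule. Lifting the exclusions for everything at the fracture site would turn the normal course of recovery into AEs, possibly in every patient.

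SAP 3.6 describes surgical imaging in the past tense, so an amendment may come too late for some patients. For those already implanted, reconcile the local and central reads against the AE database before lock and query causality for any unrecorded healing failure.

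The cost is one protocol sentence, which needs review and approval as an amendment (Protocol 13.2), a matching SAP edit, and one reconciliation step. A few more AEs may be recorded, so the safety tables may look slightly less favourable.
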